9.2.4 Concomitant Medication

Medications that the Subject may have been taking prior to study enrollment for conditions unrelated to the treatment of knee osteoarthritis, other than analgesics including NSAIDs, may be continued as long as they will not interfere with study assessments. If the Subject was taking oral glucosamine and/or chondroitin sulfate products for the treatment of knee OA prior to signing the ICF, the products may be continued, but the Subject must maintain a stable regimen for the duration of the study.

9.2.5 Restricted Medications

All analgesics other than acetaminophen are prohibited during the study. This includes, but is not restricted to, NSAIDs, opioids and topical agents for treatment of OA in the Index knee. Topical corticosteroids are allowed at any other site other than the Index knee. The analgesic medication use will be monitored at each Subject visit through review of the Subject Electronic Diary.

The use of IA injection of steroids in any joint and the use of IA injection of viscosupplements in the knee joint is prohibited throughout the study. The use of immunosuppressive agents such as cyclosporine, methotrexate are prohibited throughout the study.

9.2.6 Rescue Medications

Acetaminophen (up to a maximum of 3.0 grams per day per the package insert or as per regional limitations) will be allowed as the rescue medication for the treatment of joint pain for the duration of the study. At least forty-eight hours prior to the Baseline Visit and each follow-up visit the Subject should discontinue use of the Rescue Medication.

At the Screening Visit, the Rescue Medication (i.e. acetaminophen) will be dispensed. The Subject should be instructed to bring the Rescue Medication with them to each follow-up visit for a pill count. Additional Rescue Medication (i.e. acetaminophen) will be dispensed as needed at the follow-up visits.

A medication is considered concomitant if taken after signing the ICF and up to and including the last follow-up visit. Data on medications will include: medication name, dose, unit, route, frequency, start date, stop date, indication and whether the medication was taken for an AE.

At each study visit, the Subject will be asked about any new medications that were started since the last visit. Indications for any new medications during the study period will be recorded as AEs, unless the medications are administered for a pre-existing condition.

Anika Therapeutics, Inc. Cingal 19-01

9.2.7 Physical Exam (PE)

The PE will be performed at the time points included in Section 9.1 Schedule of Events. The PE will include an assessment of general appearance, chest and lungs, heart, abdomen, skin, musculoskeletal system, neurologic systems and other (as applicable). This PE will include an assessment of height and weight for calculation of a BMI.

9.2.8 Vital Signs

Vital signs (blood pressure, pulse, temperature) will be collected at the time points included in Section 9.1 Schedule of Events.

9.2.9 Physical Evaluation of Knees

The Blinded Evaluator will perform the Physical Evaluation of the knees at the time points included in Section 9.1, Schedule of Events. This will include assessment of effusion grade of both knees (none, mild, moderate or marked), symptoms (e.g. persistent knee pain, limited morning stiffness and reduced function) and signs (crepitus, restricted movement and bony enlargement). Knee circumference in centimeter will also be measured in both knees.

9.2.10 Range of Motion (ROM)

The Blinded Evaluator will assess the maximum ROM flexion and extension in degrees using a goniometer at the time points included in Section 9.1, Schedule of Events. The ROM will be documented as a hyphenated number. For instance, normal ROM in the knee is about 0-140 degrees.

9.2.11 Pregnancy Test

For females of childbearing potential, a urine or blood pregnancy test will be performed at the Screening Visit. Women who can confirm that they are surgically sterile or have been postmenopausal for at least 1 year prior to signing the ICF need not undergo a pregnancy test.

9.2.12 Chemistry/Hematology/Urinalysis

For all subjects, the blood / urine tests in Table 1 will be performed to assist in assessing Subject eligibility at the Screening Visit. A routine and microscopic analysis of the urine will be conducted at the Screening Visit.

Subjects will be eligible to repeat screening after a minimum of 14 days at the discretion of the Investigator and with approval of the Sponsor.

Table 1 Laboratory Analytes									
Hematolog	ЭУ	Clinica	l Chemistry	Urinalysis					
Hematocrit MCV		Sodium Triglycerides		рН	Blood				
Hemoglobin	мсн	Potassium	Calcium	Specific Gravity	Leukocytes				
Red Blood Cell (RBC) count	мснс	Chloride	AST/SGOT	Osmolality	Bilirubin				
White Blood Cell (WBC) count		Glucose	ALT/SGPT	Clarity	Ketones				
Differential WBC count		Urea nitrogen	Alkaline Phosphatase	Color	Urobilinogen				
Platelet count		Creatinine	Total protein	Protein	Nitrites				
HbA1c (for diabetics only)		Total bilirubin	Albumin	Glucose					

The clinical laboratory will clearly mark all laboratory test values that are outside the normal range and the Investigator will indicate which of these deviations are clinically significant. Any clinically significant observations in results of clinical laboratory are to be recorded as part of the patient's medical history if observed as part of the screening laboratory results.

9.2.13 Rater Training

Prior to completing any of the patient reported assessments, Subjects will complete rater training in two parts:

9.2.13.1 Accurate Pain Reporting (APR)

The Accurate Pain Reporting training instructs subjects how to accurately and reliably report pain scores, and on the proper use of pain scales, with the aim of increasing subjects' pain reporting accuracy. Subjects receive training as indicated in the Schedule of Events.

9.2.13.2 Placebo Response Reduction (PRR)

The Placebo Response Reduction training teaches appropriate expectations of personal benefit while participating in a clinical trial. The purpose is to provide subjects truthful information that will neutralize the typically excessive expectations that drive high placebo responses in clinical studies. Subjects receive training as indicated in the Schedule of Events.

9.2.14 WOMAC

The WOMAC index is self-administered and assesses the three dimensions of pain, disability and joint stiffness in knee and hip osteoarthritis using a battery of 24 questions (5 pain, 2 stiffness, 17 physical

function) [23] (see Appendix 1). This trial will utilize the VAS version of the WOMAC index on the Electronic Patient Reported Outcomes (ePRO) system provided to the investigational sites. The Subject will be trained on how to complete the WOMAC which will be collected at the time points indicated in Section 9.1.

9.2.15 Visual Analog Scale (VAS) Pain Score

During the site visits, the Subject will report pain related to the index and contralateral knee measured with a 0-100 mm Visual Analog Scale (VAS) Scale (see Appendix 2).

9.2.16 Numerical Rating Scale (NRS) Pain Score

During the site visits, the Subject will report pain related to the index and contralateral knee measured with a 0-10 Numerical Rating Scale (see Appendix 3).

9.2.17 EuroQoL EQ-5D

Outcomes information from the subject-completed EuroQoL EQ-5D will be obtained at all evaluation points specified in Section 9.1, Schedule of Events [24, 25] (see Appendix 5). The EQ-5D is a standardized measure of health status developed by the EuroQoL Group which is applicable to a wide range of health conditions and treatments. The EQ-5D provides a simple descriptive profile and a single index value for health status that can be used in the clinical and economic evaluation of health care as well as in population health surveys [24].

The EQ-5D is designed for self-completion by respondents and consists of 2 pages - the EQ-5D descriptive system and the EQ Visual Analog Scale (EQ VAS). The EQ-5D descriptive system comprises the following 5 dimensions: mobility, self-care, usual activities, pain/discomfort and anxiety/depression [24]. The Subject is asked to indicate his/her health state by ticking (or placing a cross) in the box against the most appropriate statement in each of the 5 dimensions. The EQ VAS records the subject's self-rated health on a vertical VAS where the endpoints are labeled 'Best health you can imagine' and 'Worst health you can imagine'. This information is used as a quantitative measure of health outcome as judged by the individual respondents [24].

This trial will utilize the EQ-5D on the ePRO system provided to the investigational sites.

9.2.18 Patient Global Assessment

The Patient Global Assessment (see Appendix 4) is a VAS that will be completed by the Subject at time points specified in Section 9.1, Schedule of Events, to determine the Patient Global Assessment of response to therapy score. "Considering all the ways the osteoarthritis in your study knee affects you, what is your assessment of how much your study knee is bothering you today?"

This trial will utilize the Patient Global Assessment on the ePRO system provided to the investigational sites.

9.2.19 Evaluator Global Assessment

The Evaluator Global Assessment (see Appendix 4) will be completed by the Blinded Evaluator at the time points delineated in Section 9.1, Schedule of Events. To reduce the potential for bias, it is important for the Blinded Evaluator to complete the Evaluator Global Assessment prior to collecting the Patient Global Assessment.

The Blinded Evaluator will be asked "Considering all the ways the osteoarthritis in the patient's Index knee affect him/her, what is your assessment of how much the patient's knee is bothering him/her today?"

This trial will utilize the Evaluator Global Assessment on the ePRO system provided to the investigational sites.

9.2.20 Subject Electronic Diary / Patient Reported Outcome ePRO

The Subject will be provided with an electronic application "app" or an electronic device to utilize as a Subject Electronic Diary. This will be provided at the Screening Visit and the Subject will receive training on when and how to complete the Subject Electronic Diary. The Subject Electronic Diary will be used to collect information on daily pain scores using VAS and NRS scales; medication usage including rescue medications; concomitant therapies (e.g. physical therapy) and AEs. The Subject Electronic Diary will be reviewed by site staff to determine if there are AEs that need to be captured within the Electronic Data Capture (EDC) system and to assess rescue medication usage and compliance with the protocol.

9.2.21 Knee X-Rays/Assessment of Kellgren-Lawrence Score

Subjects will be asked to have the following X-Rays of both knees collected at the Screening Visit:

- Long Limb Standing Anterior Posterior (AP) view
- Fixed Flexion Posterior Anterior (PA) view

These screening images will be transferred to, as well as handled by, the Central Imaging Core lab according to their Standard Operating Procedures (SOPs). An Independent Radiologist from the Central Imaging Core lab will evaluate the Screening plain films of both knees for osteoarthritic changes using the K-L scoring system (see Appendix 6) and exclude subjects with K-L severity grade of 0, I or IV in the Index knee or K-L severity grade III or IV in the contralateral knee. Additionally, varus / valgus alignment will be assessed in both knees and subjects with greater than 8 degrees of malalignment in either knee will be excluded.

The Independent Radiologist will furthermore evaluate the screening X-Rays to determine the following exclusion criteria for the Index knee:

Presence of osteochondromatosis

Cingal 19-01

- History of ACL repair, reconstruction or injury
- History of cartilage repair surgery
- X-Ray findings of acute fracture(s)
- Severe loss of bone density
- Avascular necrosis
- Severe bone or joint deformity in the Index knee
- Advanced cases of gout
- Advanced cases of Paget
- Acromegaly
- Osteochondritis dissecans

The Independent Radiologist will confirm the eligibility of screened subjects based on the imaging enrollment criteria. In the event the Independent Radiologist determines that a Subject is ineligible based on an imaging finding, the decision of the Independent Radiologist will prevail.

All the Screening X-Rays are paid for by this research study and are free of charge to the subject.

The images acquired for this trial will be transferred from the imaging site to the Central Imaging Core lab electronically and uploaded to EDC. The X-Rays will be identified by the subject's study identification (ID) number. No personal identifiable information will be included on the image.

9.2.22 Blinding

Although the identity of the syringes will not be revealed, it is recognized that there is a visible difference in the Clinical Trial Material (CTM) in the syringes as well as a difference in the extrusion force among Cingal[®], Triamcinolone Hexacetonide (TH), and Placebo and also a difference in volume. To maintain the double-blind design (Blinded Evaluator, Subject) of the study, the following measures will be taken. To maintain the blind of the subject, a drape will be used to shield the view of the subject, or the patient will be positioned in such a manner, that they cannot observe the syringe or injection. Furthermore, due to the lack of proprioceptive receptors in the cartilage of the knee [26], the Subject should not be able to detect the viscosity or volume of the CTM being injected.

The Treating Physician will be aware of the differences and will be unblinded, therefore; there will be a **Treating Physician** (unblinded) and a **Blinded Evaluator** (blinded) at each site with clearly defined roles.

- Treating Physician: The Treating Physician is most often the Pl. He/she will administer the Cingal, TH, or Placebo injection but will not participate in the efficacy evaluation.
- Blinded Evaluator: The Blinded Evaluator will be a physician, research nurse, registered physiotherapist or physician assistant trained by the PI to perform the assessments outlined in the protocol. The Blinded Evaluator will complete the Physical Exam, Physical Evaluation of both knees, Range of Motion (ROM) assessment of both knees, and the Evaluator Global

Assessment.

9.3 Screening

Each Subject will indicate his or her willingness to participate in the study by signing the ICF. Subjects will receive a unique Subject ID (e.g., 100-001) where the first three digits represent the number assigned to the investigative site and the last three digits represent the Subject number. The number will be recorded on the Enrollment Log and in the subject's electronic Case Report Forms (eCRFs). Subjects will be identified by the unique Subject ID for the duration of their participation in the study.

The following screening and eligibility data will be collected 14 ±3 days prior to the Baseline/Treatment Visit:

- Informed Consent
- Demographics (age, gender, race, and ethnicity)
- Medical History
- Assess Concomitant Medications
- Physical Examination including BMI and Vitals
- Physical Evaluation of Both Knees to be performed by Blinded Evaluator
- Range of Motion Evaluation of Both Knees to be performed by Blinded Evaluator
- Evaluator Global Assessment to be performed by Blinded Evaluator
- Pregnancy Test (women of childbearing potential)
- Screening Laboratory Testing
 - o Chemistry
 - Hematology
 - Urinalysis
- Rater Training
- WOMAC Pain Scale (Both Knees)
- VAS Pain Scale (Both Knees) taken at Screening and daily until the Baseline visit using Subject Electronic Diary
 - NRS Pain Scale (Both Knees) taken at Screening and daily until the Baseline visit using Subject Electronic Diary
- EuroQoL 5D-5L
- Patient Global Assessment
- Bilateral Knee X-Ray and Assessment of K-L Severity Grade
- Review of X-Rays by Independent Radiologist
- Distribute Subject Electronic Diary
- Dispense Rescue Medication
- Rescue Medication will be recorded between Screening and Baseline visit using Subject Electronic Diary
- Assessment of Screening Enrollment Criteria

Anika Therapeutics, Inc. Cingal 19-01

During the Screening Visit inform the Subject about discontinuation of all analgesics including NSAIDs except acetaminophen. Acetaminophen will be used as a Rescue Medication (Pain Control) through the completion of the study, however; acetaminophen should be discontinued at least 48 hours before each follow-up study visit. Subjects who are taking oral glucosamine and chondroitin sulfate products should be informed that a stable dose of these supplements must be maintained for the duration of the study.

Subjects who fail to meet screening eligibility criteria may, at the discretion of the Investigator and with Sponsor approval, be rescreened after a minimum of 14 days post- screening. A new Subject number will be assigned.

9.4 Baseline

The Baseline Visit will occur 14±3 days after the Screening Visit. The following assessments will take place during this visit:

- Concomitant Medications
- Confirm Rescue and Prohibited Medication Washout
- Count/Dispense Rescue Medication Pills
- Evaluate Subject Electronic Diary including daily pain scores
- Physical Evaluation (Both Knees) to be performed by Blinded Evaluator
- Range of Motion (Both Knees) to be performed by Blinded Evaluator
- Evaluator Global Assessment to be performed by Blinded Evaluator
- WOMAC (Both Knees)
- VAS Pain Scale (Both Knees)
- NRS Pain Scale (Both Knees)
- EuroQoL-5D-5L
- Patient Global Assessment
- Randomization if Subject meets all Screening and Baseline assessments (except IA aspiration)
- Aspirate Synovial Fluid
- Evaluation of Baseline Enrollment Criteria
- Intra-articular Injection to be performed by Treating Physician
- Assess Treatment-Emergent Adverse Events

9.5 Pre-Treatment Screening

Evaluate the Subject for the Baseline enrollment criteria regarding the WOMAC and ROM. Section 9.2

9.6 Randomization

If the Subject has met the Screening and Baseline enrollment criteria (except assessment of IA fluid), he/she will be randomized using the EDC system. The EDC system will indicate which blinded carton should be used for that injection using a kit number (________).

9.7 Treatment

The Treating Physician will prep and drape the subject's Index knee. The Treating Physician will always perform the Index knee injection for each Subject and will not participate in the efficacy evaluation.

Using a sterile syringe and an 18-21 gauge needle, the Treating Physician should penetrate the joint space, aspirate to dryness and retain any synovial fluid for measurement of volume and laboratory analysis (if needed). Aspiration should be attempted on all subjects, regardless of whether there is clinical appearance of effusion.

Evaluate the Subject for the Baseline Enrollment Criteria regarding the volume and appearance of the synovial fluid aspirate. If needed, the aspirate should be sent for microscopic examination and results evaluated prior to the injection. The injection should be postponed until the results of the microscopic examination are received and the Treating Physician determines it is safe to proceed with the study injection. Any Subject found to not meet the inclusion/exclusion criteria will be excluded from the study. If this possibility is anticipated, an alternate plan for treatment should be pre-arranged.

For the TH arm, an ampoule of Triamcinolone Hexacetonide will be provided by the Sponsor as CTM. The Treating Physician will draw the TH into an empty syringe as standard practice for an IA injection.

Once the synovial fluid characteristics and volume are confirmed to be acceptable, the Treating Physician should inject the entire contents of the syringe into the joint space unless this volume is felt to be too much. The Treating Physician should advise each Subject to avoid heavy physical activities (including jogging, tennis, heavy lifting, prolonged standing) for 24 hours after the study injection.

The Blinded Evaluator must not be present for the injection.

9.8 Injection Technique

It is recommended that a lateral midpatellar injection be performed in accordance with the findings of Jackson et al. (2002) who demonstrated a greater rate of injection accuracy when compared to anterolateral and anteromedial injections [27]. Because this study is enrolling subjects with K-L II and III in the Index knee, it should be noted that in a study by Toda et al (2008), it was found that the best injection approach may be determined by the severity of knee OA [28]. However, each treating physician may utilize the preferred method of injection based on their clinical practice.

To perform a lateral midpatellar injection, the lower limb is extended on the examination table. The patella will be manually everted and moved laterally by the physician's free hand. The needle will be

advanced transversely between the articular surfaces of the patellofemoral joint at the midpoint of the patella [27].

[figure not shown]

Diagram showing the lateral midpatellar portal [27] P = patella,F = femur, T = tibia, and FP = fat pad.

Post-Treatment Assessments and Instructions

Prior to leaving the clinic, the Subject should be evaluated for local and non-local AEs and the Index knee assessed for local AEs. All post-treatment signs and symptoms that are unexpected should be recorded as AEs. The expected appearance of the Index knee should be discussed with the Subject with a request that all unexpected symptoms be reported to a member of the study team.

Subjects who exhibit significant complications, (e.g., significant inflammation or significant swelling of the joint) may warrant diagnostic or therapeutic procedures as determined by the Treating Physician in conjunction with the Blinded Evaluator. All subjects will be evaluated for safety for the duration of their participation in the study. Inclusion of the Subject in the efficacy evaluation will be decided on a case by case basis.

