6.4 Safety Endpoint

The incidence, timing, severity, and relationship to treatment of all AEs will be collected and coded using MedDRA. Local injection site and non-local events will be recorded separately.

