10.5 Reporting

10.5.1 Adverse Events

Only AEs that occur during and after treatment (treatment emergent AEs) will be recorded. At each visit during the trial, AEs that have occurred since the previous visit must be recorded. All subjects will be questioned and evaluated for AEs or complications associated with the procedure. Complications of the injection include, but are not necessarily limited to: pain, swelling and/or inflammation at the injection site. The Investigator will determine the severity and relationship of each event, as defined above.

AEs observed during the course of this study, regardless of severity or relationship to the injection will

be recorded on the appropriate eCRF. Each reported complication/AE will also include the duration, action taken to address the AE, and the resolution status (e.g. ongoing, resolved). These subjects will continue to be evaluated for safety and efficacy at all scheduled follow-up points.

The Sponsor must report the results of an evaluation of an Unanticipated Adverse Device Effect (UADE) to relevant regulatory agencies and all reviewing IRBs and Investigators within timelines required by the regulatory agencies.

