13.3.2 Anticipated Adverse Reactions

Reported adverse reactions associated with the IA use of combined Hyaluronic Acid and Triamcinolone Hexacetonide:

Single intra-articular injections of sodium hyaluronate combined with Triamcinolone Hexacetonide has been studied by Anika Therapeutics, Inc. in two Phase III clinical trials: Cingal 13-01, 16-02 and additionally the 39-week extension trial: Cingal 17-02

The most common reported adverse events associated are the following: arthralgia, joint swelling, warmth, range of motion decrease and injection site pain.

Incidences of rash, headache, dizziness, chills, hives, itching, nausea, muscle cramps, peripheral edema, and malaise have also been reported in association with intra-articular injections.

In Cingal 13-01, 16-02, and 17-02 the AEs that were possibly, probably and definitely related to the study injection for patients receiving Cingal were 2.0%, 7.6% and 0 % respectively [14-16]. These AEs were minor or moderate complications that required little or no treatment. These included injection site events, joint swelling, joint pain, and limb pain.

Reported adverse reactions associated with the IA use of corticosteroids:

Single intra-articular injections of Triamcinolone Hexacetonide have been associated with the following adverse reactions:

- Dermatologic: Whitening of the skin at the injection site, local fat atrophy.
- Musculoskeletal: Joint infection, joint swelling and pain several hours after injection, tendon rupture, pain, swelling, ligament damage.
- Neurological: Nerve damage.

• General: Infection, local bleeding, allergic reactions.

Anika Therapeutics, Inc. has conducted one Phase III trial utilizing Triamcinolone Hexacetonide (Lederlon) in Cingal 16-02 and additionally the 39-week extension trial: Cingal 17-02 [14, 15]. The AEs that were possibly, probably and definitely related to the study injection for patients receiving Triamcinolone Hexacetonide were 4.1% and 0 % respectively. These AEs were minor or moderate complications that required little or no treatment. These involved injection site pain and joint pain.

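### Protocol 9.8 ties injection-day AE recording to unexpectedness, against the all-AE rule in 10.5.1, so common local reactions can go unrecorded

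*Protocol*

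**What the plan says.** Protocol 9.8, in the part on post-treatment assessments, opens with an unrestricted check: "Prior to leaving the clinic, the Subject should be evaluated for local and non-local AEs and the Index knee assessed for local AEs". The next sentence adds a condition: "All post-treatment signs and symptoms that are unexpected should be recorded as AEs". Subjects are then told how the knee is expected to look, "with a request that all unexpected symptoms be reported to a member of the study team".

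Protocol 10.5.1 sets the general recording rule. The window is "Only AEs that occur during and after treatment (treatment emergent AEs) will be recorded", which includes injection day. The rule applies to "AEs observed during the course of this study, regardless of severity or relationship to the injection will" be entered on the eCRF. The section also names the local reactions of interest: "Complications of the injection include, but are not necessarily limited to: pain, swelling and/or inflammation at the injection site".

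The safety endpoint in Protocol 6.4, repeated in SAP 3.4, is: "The incidence, timing, severity, and relationship to treatment of all AEs will be collected and coded using MedDRA". Both sections add that local and non-local events are kept apart. Protocol 11.7 and SAP 4.4 then tabulate local against non-local events.

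Protocol 10.2 defines unexpected as not listed in the Investigator's Brochure. Protocol 13.3 presents its lists as Brochure content, and 13.3.2 says of the combined product: "The most common reported adverse events associated are the following: arthralgia, joint swelling, warmth, range of motion decrease and injection site pain".

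**The concern.** Two recording rules apply to the same hours of the same day. One depends on whether the finding was expected and the other does not, and no section says which governs. In 10.2, expectedness classifies an AE and helps decide whether it is a SUSAR. It is not a test of whether the AE is written down. Section 9.8 uses it as that test.

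The condition falls on the events that the local-event tables are there to count. If some sites apply 9.8 and others 10.5.1, the local AE rate is too low overall, and it varies between sites for reasons unrelated to the products. A short-lived reaction that was never recorded cannot be recovered at analysis.

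**Working it through.** The documents give no figure for this point, so the check is mainly a comparison of texts.

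**Step 1: is there a conflict?**

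| Section | Which events | Expectedness condition |
|---|---|---|
| 9.8, first sentence on AEs | Local and non-local AEs before discharge | None |
| 9.8, recording sentence | Post-treatment signs and symptoms | Unexpected |
| 9.8, subject instruction | Symptoms subjects are asked to report | Unexpected |
| 9.4 | TEAE assessment, listed after the injection | None |
| 10.5.1 | AEs during and after treatment, whatever their severity or relationship | None |
| 6.4 and SAP 3.4 | All AEs | None |

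Two sentences of 9.8 carry a condition that no other section has.

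**Step 2: what does the condition exclude?** By 10.2, an event listed in the Brochure is expected. By 13.3 and 13.3.2, the commonest local reactions are listed there. Those reactions therefore fall outside the 9.8 recording sentence. They overlap with the injection-site pain, swelling and inflammation that 10.5.1 names as complications.

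**Step 3: would later capture make up for it?**
- Section 13.3.2 describes swelling and pain several hours after a TH injection, and section 4 calls related AEs in the earlier trials transitory.
- The next visit is at 1 week ± 3 days, that is, 7 − 3 = 4 to 7 + 3 = 10 days later. It includes AE assessment, evaluation of both knees and ROM of the index knee.
- The diary (9.2.20) collects AEs with no expectedness limit, and site staff review it to decide which need entering in EDC.

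These routes would recover some events. A reaction that settled within a day or two, in a subject asked to report the unexpected, could still be missed.

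**Step 4: scale only.** Inputs are the arm size of 99 (11.1) and the earlier related-AE rates (13.3.2). Expected subjects = arm size × rate.
- Cingal, lower rate: 99 × 0.020 = 1.98, about 2.0
- Cingal, higher rate: 99 × 0.076 = 7.52, about 7.5
- TH: 99 × 0.041 = 4.06, about 4.1
- The extension study had 0% in both arms, which gives 0.

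These rates cover whole trials. The share that were expected local reactions on injection day is not given. As an assumption, suppose a share s goes unrecorded, so that recorded = expected × (1 − s):

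| s | Cingal at 2.0% | Cingal at 7.6% | TH at 4.1% |
|---|---|---|---|
| 0 | 2.0 | 7.5 | 4.1 |
| 25% | 1.5 | 5.6 | 3.0 |
| 50% | 1.0 | 3.8 | 2.0 |
| 75% | 0.5 | 1.9 | 1.0 |
| 100% | 0 | 0 | 0 |

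The table shows that counts are small enough for a few missed subjects to matter. It does not estimate how many would be missed.

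**The case against.** The best defence is that 9.8 does not stand alone. It never uses the word only, and it never says that expected findings are to be left out. Its own preceding sentence asks for an AE evaluation without any filter. Section 9.4 lists TEAE assessment after the injection, and the Schedule of Events marks AE assessment at Baseline. The dedicated AE section, 10.5.1, is unconditional. The diary and the week 1 visit follow. A site that works from 10.5.1 would capture these events.

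The meaning of unexpected in 9.8 can also be argued. The 10.2 definition is written for drug AE classification. Section 9.8 uses the word beside the expected appearance of the knee, which might mean no more than ordinary needle-site findings.

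Much of this stands. It rules out the reading that 9.8 is the sole injection-day check, or that local reactions will as a matter of course go unrecorded. It does not remove the conflict. The recording sentence narrows the evaluation sentence before it, no section gives 10.5.1 precedence, and even the milder meaning exempts findings that 10.5.1 does not.

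A reader might also infer that the undercount would differ by arm, because the Synopsis gives 4 mL for Cingal and saline but 1 mL for TH, and the Treating Physician is unblinded. The documents do not support that. Section 7.2 has the Blinded Evaluator collect and record AEs, section 9.7 keeps that person out of the injection, and nothing says that expectedness is judged by injected volume.

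**Conclusion.** The point holds as an internal contradiction with a plausible effect on the safety data. A site that follows 9.8 literally can leave the commonest transient local reactions on injection day unrecorded, against 10.5.1 and the all-AE endpoint. Local-event counts could then be too low and could differ between sites.

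This rests on two assumptions: that some sites would work from 9.8, and that they would read unexpected as 10.2 defines it or in a similar everyday sense.

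The size of the loss cannot be derived from the documents. A reader might infer from the small counts that the observed rate would be halved or the Cingal–TH comparison reversed. That follows only if a chosen number of subjects is removed from one arm, and no figure in the documents supports such a removal.

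**What to change.** In Protocol 9.8, delete the restriction to unexpected findings. State that all new or worsened post-treatment signs and symptoms are recorded as AEs under 10.5.1, with expectedness classified separately under 10.2. Change the subject instruction so that all new or worsened symptoms are to be reported. The words new or worsened are needed: a request for every symptom would bring in pre-existing OA pain, which the daily VAS and NRS scores already capture.

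The cost is two wording changes in one section and matching site training. Sites will make more minor AE entries, and the reported local AE rate may be slightly higher. The change concerns data recording only and should be in place before subjects are treated.
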